8.2 Statistical Analysis Plan

Toxicities will be summarized as the number and percentage of patients with each type of toxicity. Responses will be summarized as frequencies and percentages. The Kaplan Meier methods will be used to estimate overall survival and progression free survival. Outcomes will be calculated from the date of study entry to the date of the corresponding event.

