2.1.2.1 Safety assessments during the Phase II expansion

This investigator initiated study will be under the oversight of the Fred Hutchinson/University of Washington Cancer Consortium IRB and Data and Safety Monitoring committee. The investigators are ultimately responsible for monitoring the safety of patients who have entered this study and for alerting the Consortium IRB to any event that seems unusual in accordance with IRB policy. The investigator is responsible for the appropriate medical care of patients during the study. The investigator remains responsible to follow, through an appropriate health care option, adverse events that are serious or that caused the patient to discontinue before completing the study. The patient should be followed until the event resolves or stabilizes. Frequency of follow-up is left to the discretion of the investigator.

Safety measurements that will be used in the study include physical examinations and clinical laboratory tests (hematology and blood chemistries). The adverse event will be graded for toxicity using the NCI CTC version 4.0. Toxicity assessment will occur at the start of each cycle, or more frequently if clinically indicated. Any adverse events leading to a treatment interruption or dose reduction along with all adverse events that are grade 3 and higher will be recorded in the CRF. Adverse Events that meet Merck's definition of Event of Clinical Interest (refer to the Pembrolizumab ECI guidance document) will also be recorded.

The criteria for dose de-escalation for adverse events are outlined in Section 5.2. Any patient who requires two dose modifications or de-escalations will be taken off study.

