- A new course of treatment may begin on the scheduled Day 1 of a new cycle if all non-hematological toxicity from the previous cycle has recovered to ≤ Grade 1 or baseline, and/or hematologic recovery documented as outlined in section 5.2.1.4.

Initiation of subsequent cycles of therapy may be delayed for up to 12 weeks to allow recovery from all drug-related toxicity. Alternately, the Investigator may choose to administer supportive care (blood product transfusions) for retreatment criteria to be met. If the recovery criteria are not met after a 12-week delay, the patient will be discontinued from study treatment unless, in the opinion of the Investigator, the patient is experiencing a clinical benefit, in which case a decision regarding continuation of treatment will be made on an individual patient basis in consultation with the Merck medical monitor. Justification will be recorded in the source documents.

When initiating a subsequent cycle, a minimum interval of 21 days should be observed between MK-3475 administrations (with no minimum interval for vorinostat).

Continuation of study therapy during a cycle:

Within any cycle, the dose/schedule of either study drug may be adjusted as necessary.

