7.1.2 Clinical Procedures/Assessments

7.1.2.1 Adverse Event (AE) Monitoring

The investigator or qualified designee will assess each subject to evaluate for potential new or worsening AEs as specified in the Trial Flow Chart and more frequently if clinically indicated. Adverse experiences will be graded and recorded throughout the study and during the follow-up period according to NCI CTCAE Version 4.0 (see Section 12.2). Toxicities will be characterized in terms regarding seriousness, causality, toxicity grading, and action taken with regard to trial treatment.

All AEs of unknown etiology associated with MK-3475 exposure should be evaluated to determine if it is possibly an event of clinical interest (ECI) of a potentially immunologic etiology (irAE). See Section 5.6.1.1 and the separate guidance document in the administrative binder regarding the identification, evaluation and management of AEs of a potential immunological etiology.

Please refer to section 7.2 for detailed information regarding the assessment and recording of AEs.

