7.1.5.3 Post-Treatment Visits

7.1.5.3.1 Safety Follow-Up Visit

The mandatory Safety Follow-Up Visit should be conducted approximately 30 days after the last dose of trial treatment or before the initiation of a new anti-cancer treatment, whichever comes first. All AEs that occur prior to the Safety Follow-Up Visit should be recorded.

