7.2 Assessing and Recording Adverse Events

An adverse event is defined as any untoward medical occurrence in a patient or clinical investigation subject administered a pharmaceutical product and which does not necessarily have to have a causal relationship with this treatment. An adverse event can therefore be any unfavorable and unintended sign (including an abnormal laboratory finding, for example), symptom, or disease temporally associated with the use of a medicinal product or protocol-specified procedure, whether or not considered related to the medicinal product or protocol-specified procedure. Any worsening (i.e., any clinically significant adverse change in frequency and/or intensity) of a preexisting condition that is temporally associated with the use of the Merck's product, is also an adverse event.

Changes resulting from normal growth and development that do not vary significantly in frequency or severity from expected levels are not to be considered adverse events. Examples of this may include, but are not limited to, teething, typical crying in infants and children and onset of menses or menopause occurring at a physiologically appropriate time.

Merck product includes any pharmaceutical product, biological product, device, diagnostic agent or protocol-specified procedure, whether investigational (including placebo or active comparator medication) or marketed, manufactured by, licensed by, provided by or distributed by Merck for human use.

Adverse events may occur during the course of the use of Merck product in clinical trials or within the follow-up period specified by the protocol, or prescribed in clinical practice, from overdose (whether accidental or intentional), from abuse and from withdrawal.

Adverse events will be recorded from the time the first dose of either vorinostat or MK-3475 is administered through 30 days following cessation of treatment and at each examination on the Adverse Event case report forms/worksheets. After 30 days, adverse events related to either MP-3475 or vorinostat will be followed until resolution or stabilization of the AE or until the beginning of a new anti-neoplastic therapy, whichever occurs first. The reporting timeframe for adverse events meeting any serious criteria is described in section 7.2.3.1.

Only adverse events that meet the following definition will be recorded.

- All grade 3 and higher adverse events

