7.2.4 Evaluating Adverse Events

An investigator who is a qualified physician will evaluate all adverse events according to the NCI Common Terminology for Adverse Events (CTCAE), version 4.0. Any adverse event which changes CTCAE grade over the course of a given episode will have each change of grade recorded on the adverse event case report forms/worksheets.

All adverse events regardless of CTCAE grade must also be evaluated for seriousness.

Product: MK-3475 **Protocol/Amendment No.:**

Table 10 Evaluating Adverse Events

An investigator, who is a qualified physician, will evaluate all adverse events as to:

V4.0 CTCAE Grading	Grade 1	Mild; asymptomatic or mid symptoms; clinical or diagnostic observations only; intervention not indicated.						
	Grade 2	Moderate; minimal, local or noninvasive intervention indicated; limiting age-appropriate instrumental ADL.						
	Grade 3	Severe or medically significant but not immediately life-threatening; hospitalization or prolongation or hospitalization indicated;						
		disabling; limiting self-care ADL.						
	Grade 4	Life threatening consequences; urgent intervention indicated.						
	Grade 5	Death related to AE						
Seriousness	A serious adverse	event is any adverse event occurring at any dose or during any use of Merck product that:						
	†Results in death							
	†Is life threatenin	ng; or places the subject, in the view of the investigator, at immediate risk of death from the event as it occurred (Note: This does not include an						
	adverse event that	, had it occurred in a more severe form, might have caused death.); or						
	†Results in a pers	sistent or significant disability/incapacity (substantial disruption of one's ability to conduct normal life functions); or						
	†Results in or prolongs an existing inpatient hospitalization (hospitalization is defined as an inpatient admission, regardless of length of stay, even if the hospitalization is a precautionary measure for continued observation. (Note: Hospitalization [including hospitalization for an elective procedure] for a preexisting condition which has not worsened does not constitute a serious adverse event.); or							
	†Is a congenital anomaly/birth defect (in offspring of subject taking the product regardless of time to diagnosis);or							
	Is a new cancer: (that is not a condition of the study) or							

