10.6 Data Management

The Protocol Director, or her designees, will prepare and maintain adequate and accurate participant case histories with observations and other data pertinent to the study. Original source documents should be transcribed to Case Report Forms (CRFs) and used to analyze the study data. Source documents include hospital records, clinical charts, laboratory and pharmacy records, and recorded electronic data.

All data required by the trial will be entered onto paper and electronic case report forms. Any corrections to data required into the paper case report forms must be made in such a way that the original entry is not obscured. Only designated study staff will enter data for study participants after study visits. Case report forms will be checked against source document data by study staff.

Trial oversight will be carried out by the Protocol Director, [name], and her research staff. They will meet weekly to review recently acquired data and adverse events. The data recorded within the research charts and protocol database is compared with the actual data that is available from the medical record and/or clinical histories. Data detailed in the research case report forms includes the nature and severity of all toxicities, which are also reported as described above. All investigators on the protocol will receive formal training in the ethical conduct of human research. Institutional support of trial auditing is provided in accordance with the Cancer Consortium's Data and Safety Monitoring Plan. In addition,

protocols are reviewed at least annually by the Scientific Review Committee (SRC) and the Institutional Review Board (IRB).

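### Section 8.2's toxicity percentages name no grade, and the recording rule in 7.2 drops non-serious, non-ECI grade 1–2 events without a dose action, so any-grade tolerability cannot be estimated

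*Combined protocol and SAP*

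**What the plan says.** Section 3.1 makes safety and tolerability the primary objective, and its hypothesis has two parts: the combination is safe, and it is well tolerated. Section 8.2 gives the analysis: "Toxicities will be summarized as the number and percentage of patients with each type of toxicity". It sets no grade and does not say which recorded events feed the table.

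Two sections restrict what is recorded. Section 7.2: "Only adverse events that meet the following definition will be recorded". The list that follows is grade 3 or higher, events requiring a dose reduction or delay of either drug, and ECIs. Section 2.1.2.1 gives nearly the same list for the case report form: dose-interrupting or dose-reducing events and ECIs, and "all adverse events that are grade 3 and higher will be recorded in the CRF".

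Two sections read as unrestricted. Section 7.1.5.3.1: "All AEs that occur prior to the Safety Follow-Up Visit should be recorded". Section 10.6: "Data detailed in the research case report forms includes the nature and severity of all toxicities, which are also reported as described above".

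Section 7.1.2.1 also speaks of recording without a grade limit, but then sends the reader on: "Please refer to section 7.2 for detailed information regarding the assessment and recording of AEs".

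**The concern.** Section 2.1 says the safety of the two drugs together had not been described before, and treatment may last two years. Over that time, tolerability depends largely on chronic low-grade toxicity, and the protocol acts on it. Section 5.2.2 moves vorinostat to bedtime for fatigue of grade 1 or above. Section 5.2.1.4.2 expects mild-to-moderate diarrhea that becomes more frequent with continued dosing, and asks for supportive care to be considered from grade 1.

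A table of the percentage of patients with each toxicity will normally be read as how often that toxicity occurred. Under 7.2, the fatigue, nausea and diarrhea rows would mostly hold grade 3+ or dose-changing cases, and nothing in 8.2 warns the reader. Events that are never entered could be recovered only by chart review.

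**Working it through.** **1. Which recording rule governs.** Section 7.2 is specific, uses the word only, is echoed by 2.1.2.1 and is cross-referenced by 7.1.2.1. Its recording window runs to 30 days after treatment stops. The visit in 7.1.5.3.1 falls at about 30 days, so that sentence can be read as setting a time window. The sentence in 10.6 ties itself back to reporting described elsewhere. Section 7.2 is the best reading; the other two sections are loosely worded.

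**2. What 7.2 keeps and loses.**

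| Event | Entered? | Basis |
|---|---|---|
| Grade 3 or higher | Yes | 7.2; 7.2.4 |
| Reduces or delays a dose, any grade | Yes | 7.2 |
| ECI, including grade 2 pneumonitis | Yes | 7.2, 7.2.3.2 |
| Serious, any grade | Reported | 7.2.3.1 |
| DLT | Yes: every criterion in 2.1.1.1 rests on grade 3+, a cycle delay or a dose modification | 2.1.1.1, 7.2 |
| Grade 2 non-hematologic, persisting to the next Day 1 | Yes, through the delay | 5.2.1.5 |
| Other grade 1–2, no dose action | No | 7.2 |

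Section 7.2.4 helps with the first row: "Any adverse event which changes CTCAE grade over the course of a given episode will have each change of grade recorded". A grade 3+ table can therefore be built. For the sixth row, 5.2.1.5 lets a new cycle start "if all non-hematological toxicity from the previous cycle has recovered to" grade 1 or baseline. Grade 2 fatigue is less clear: Table 3.1 handles it as grade 1, but 5.2.1.5 makes no exception for it. If it settles within the cycle without a dose change, it is not entered.

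So an ungraded 8.2 row mixes grade 3+ cases with those lower-grade cases that happened to change dosing or qualify as ECIs. It is neither an any-grade nor a grade 3+ frequency.

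**3. The plan's precision figure.** Section 8.1 says frequencies are estimated to within 17% with 35 patients. Check: 1.96 × √(0.5 × 0.5 / 35) = 0.166. It reproduces, and corresponds to 0.166 × 35 = 5.8 patients.

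**4. Effect per omitted patient.** If k patients have only unrecorded events of one type, an any-grade row falls by k/n.

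- n = 35: k = 1 gives 2.9 points; k = 6 gives 17.1; k = 10 gives 28.6.
- n = 70: k = 1 gives 1.4 points; k = 6 gives 8.6.

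Six patients in one cohort is about the size of the quoted precision. This is a comparison of scale only: that figure is sampling error, while this loss runs in one direction.

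**5. Illustration with assumed inputs.** The documents give no low-grade rates. Suppose 14 of 35 have a given toxicity at any grade: 40.0% (exact 95% interval 23.9 to 57.9).

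- k = 2: table shows 12/35 = 34.3% (19.1 to 52.2)
- k = 6: table shows 8/35 = 22.9% (10.4 to 40.1)
- k = 10: table shows 4/35 = 11.4% (3.2 to 26.7)

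More generally, if the any-grade rate is p and a share s of affected patients meets a 7.2 criterion, the table shows p × s. For assumed p of 30 to 70% and s of 10 to 50%, it shows 3 to 35%, a gap of 15 points (0.30 × 0.50) to 63 points (0.70 × 0.90).

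**6. Limiting case.** If nobody has recordable fatigue, the row reads 0/35 with exact upper limit 1 − 0.025^(1/35) = 10.0% (5.1% for 0/70), however many patients had unrecorded grade 1–2 fatigue.

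**The case against.** Restricted recording is a legitimate choice. Both drugs are approved with known single-agent profiles, and every formal safety rule (the DLT criteria and the vorinostat modification triggers) uses events that are captured. No decision in the plan depends on an any-grade rate. Section 8.2 never promises one: read with 7.2, its percentages are frequencies of recorded toxicities and are unbiased for that set. Understatement arises only if someone reads the rows as any-grade.

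The gap is also narrower than all grade 1–2 events. ECIs below grade 3 are entered, and the ECI guidance document, which is not in the file, may add more. Blood counts and chemistry are measured every cycle, so low-grade laboratory toxicity could be graded from source records, although nothing says those values go on the case report form.

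Most of this stands, and it limits the point. It does not remove it. Known single-agent profiles do not describe the combination. Good tolerability is part of the primary hypothesis, and symptomatic grade 1–2 toxicity bears on it directly. If the intended target is only the recorded set, 8.2 has to say so.

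**Conclusion.** The point holds in a limited form. On the most likely reading, with 7.2 governing, the 8.2 percentages leave out non-serious, non-ECI grade 1–2 events without a dose action. They therefore cannot support a tolerability claim at any grade. For grade 3+, dose-changing, ECI, serious and DLT counts the shortfall is zero. For rows read as any-grade its size is unknown; the figures above are arithmetic per patient and labelled assumptions, not estimates for this trial.

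A reader might infer that the safety percentages are understated throughout. The documents do not support that, because the bias exists only against an any-grade target that 8.2 does not state. A reader might also infer that two rival recording rules are in force. Sections 7.1.5.3.1 and 10.6 can both be reconciled with 7.2, so the conflict is mainly one of wording.

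**What to change.** **Preferred.** At the start-of-cycle toxicity assessments already required by 2.1.2.1, record the worst CTCAE grade of each toxicity. State that single rule in 2.1.2.1, 7.1.5.3.1, 7.2 and 10.6. In 8.2, tabulate any-grade and grade 3+ separately, by worst grade per patient. The cost is a protocol amendment and extra data entry each cycle for up to 70 patients, with no new visits.

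**If the restricted recording stays.** Point 7.1.5.3.1 and 10.6 to 7.2. Label the 8.2 tables as (a) grade 3+ and (b) dose-modifying, serious or ECI events, and state that any-grade frequencies are not estimated. This costs only wording, but gives up any-grade tolerability as a result of the trial.

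**Either way.** Use one term for a dose action. Section 2.1.2.1 speaks of interruption and 7.2 of delay, and an interruption within a cycle need not delay the next dose.

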9.0 LABELING, PACKAGING, STORAGE AND RETURN OF CLINICAL SUPPLIES

9.1 Investigational Product

The investigator shall take responsibility for and shall take all steps to maintain appropriate records and ensure appropriate supply, storage, handling, distribution and usage of investigational product in accordance with the protocol and any applicable laws and regulations.

MK-3475 Clinical Supplies will be provided by Merck as summarized in Table 11.

 Table 11-1
 Product Descriptions

Product Name & Potency	Dosage Form
MK-3475 100 mg/ 4mL	Solution for Injection

Vorinostat materials will be provided by Merck as summarized in Table 11-2

Product Name & Potency	Dosage Form	Comments
Tottinty	Dusage Fullin	Comments
Vorinostat 100 mg	capsule	Supplied Merck

9.2 Packaging and Labeling Information

Clinical supplies will be affixed with a clinical label in accordance with regulatory requirements.

9.3 Clinical Supplies Disclosure

This trial is open-label; therefore, the subject, the trial site personnel, the Sponsor and/or designee are not blinded to treatment. Drug identity (name, strength) is included in the label text; random code/disclosure envelopes or lists are not provided.

9.4 Storage and Handling Requirements

Clinical supplies must be stored in a secure, limited-access location under the storage conditions specified on the label.

Receipt and dispensing of trial medication must be recorded by an authorized person at the trial site.

Clinical supplies may not be used for any purpose other than that stated in the protocol.

Vorinostat capsules should be stored at room temperature (do not store above 30°C). Procedures for proper handling and disposal of anticancer drugs should be considered. Several guidelines on this subject have been published. There is no general agreement that all of the procedures recommended in the guidelines are necessary or appropriate.

Patients should be advised against opening or crushing vorinostat capsules. Direct contact of the powder in vorinostat capsules with the skin or mucous membranes should be avoided. If such contact occurs, wash thoroughly as outlined in the references. Personnel should avoid exposure to crushed and/or broken capsules. The clinical supplies storage area at the site should be monitored by the site staff, as per the institutional guidelines, for temperature consistency with the acceptable storage temperature range as mentioned above or in the product label attached to the protocol. Documentation of temperature monitoring should be maintained.

9.5. Vorinostat suspension preparation for patients unable to swallow capsules

Patients who are gastrostomy tube dependent will take vorinostat as a suspension prepared by the investigational pharmacy. The suspension will be prepared by mixing 20 mL of Suspensol S or OraPlus with the contents of twenty 100 mg vorinostat capsules in a 4 ounce glass bottle. After shaking bottle for 3 minutes to disperse, an additional 20 mL of OraSweet will be added, again shaken to disperse. This suspension will have a final concentration of 50mg/ml and will be stable for a maximum of 2 weeks.

9.6 Returns and Reconciliation

The investigator is responsible for keeping accurate records of the clinical supplies received from Merck or designee, the amount dispensed to and returned by the subjects and the amount remaining at the conclusion of the trial.

Upon completion or termination of the study, all unused and/or partially used investigational product will be destroyed at the site per institutional policy. It is the Investigator's responsibility to arrange for disposal of all empty containers, provided that procedures for proper disposal have been established according to applicable federal, state, local and institutional guidelines and procedures, and provided that appropriate records of disposal are kept.

10.0 ADMINISTRATIVE AND REGULATORY DETAILS

10.1 Confidentiality

Patient records will be kept in a secure location at the University of Washington accessible only to research authorized personnel. The patient identity will be kept as confidential as possible as required by law. Except as required by law, the patient will not be identified by name, social security number, address, telephone number, or any other direct personal identifier. Study subjects will be assigned an ID code. Information about the code will be kept in a secure location and access limited to research study personnel. The results of this research study may be presented at scientific or medical meetings or published in scientific journals. However, the patient identity will not be disclosed. The patient's personal data which may be included in the investigator's database shall be treated in compliance with all applicable laws and regulations.

